12.13 On-treatment (Visit 3) – Week 2, Day 15 (± 3 days)

The following procedures will be conducted at this visit:

- Ask the Patient to complete the following questionnaires: PRE-FACE (see APPENDIX 2: PRO – PRE-FACE - Signs/Symptoms and APPENDIX 3: PRO – PRE-FACE - Impacts), PGI-S (see APPENDIX 4: PRO – PGI-S), PGI-C (see APPENDIX 5: PRO – PGI-C), PGI-TS (see APPENDIX 6: PRO – PGI-TS) and PGI-SE (see APPENDIX 7: PRO – PGI-SE). All of the questionnaires should be completed prior to Investigator's assessment of signs of acne as described in section 12.20.
- Observe and query the Patient in a non-directive fashion about any AEs since the previous study visit.
- Query the Patient about any changes in concomitant therapies and medication since the previous study visit.

- Perform a Urine Pregnancy Test for all females of child-bearing potential and premenarchal (see section 12.9).
- Perform the efficacy evaluations including the Investigator's Global Assessment, inflammatory and non-inflammatory lesion counts described in sections 12.18 - 12.19.
- Perform Cutaneous Reaction Assessment and Local Tolerability Assessment as described in section 14.1 & 14.2.
- Take standardized photography of face (at selected sites, see separate photographic manual for instructions) as described in section 13.
- Review the Patient's compliance with the study requirements (review Patient diary). The Patient Diary Card will Not be collected at this visit.
- Record number of missed doses on the appropriate eCRF page.
- Review the study product application instructions with the Patient.
- Schedule/confirm the next study visit.

12.14 On-treatment Visits (Visits 4 and 5) – Weeks 4 and 8, Days 29 and Day 57 (± 3 days)

The following procedures will be conducted at these visits:

- Ask the Patient to complete the following questionnaires: PRE-FACE (see APPENDIX 2: PRO – PRE-FACE - Signs/Symptoms and APPENDIX 3: PRO – PRE-FACE - Impacts), PGI-S (see APPENDIX 4: PRO – PGI-S), PGI-C (see APPENDIX 5: PRO – PGI-C), PGI-TS (see APPENDIX 6: PRO – PGI-TS) and PGI-SE (see APPENDIX 7: PRO – PGI-SE). All the questionnaires should be completed prior to Investigator's assessment of acne as described in section 12.20.
- Observe and query the Patient in a non-directive fashion about any AEs since the previous study visit.
- Query the Patient about any changes in concomitant therapies and medication since the previous study visit.

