17.1.4 Analysis Populations

Approximately 420 male and female Patients at least 9 years of age with moderate or severe acne vulgaris with 3 or 4 [moderate to severe] on the IGA scale will be enrolled and randomized in the study with a 2:1 randomization ratio, it is anticipated that:

- 280 Patients will be randomized to receive S6G5T-3, Encapsulated Benzoyl Peroxide 3%/Encapsulated All-Trans-Retinoic Acid 0.1% Cream
- 140 Patients will be randomized to receive S6G5T-8, Vehicle Cream

The ITT population will consist of all randomized Patients who were dispensed study product. The safety population will be comprised of all randomized Patients who are presumed to have used the study product at least once and who provide at least one post-baseline safety evaluation.

An intent-to-treat (ITT) analysis will be conducted. A per-protocol (PP) analysis will also be conducted. Patients will be eligible for the PP analysis if they complete the 12-week evaluation without noteworthy study protocol violations (i.e., any Patient or Investigator activity that could have possibly interfered with the therapeutic administration of the treatment or the precise evaluation of treatment efficacy). The PP population will include Patients in the ITT population who do not meet any of the following criteria:

- Failed any of the inclusion/exclusion criteria;
- Have taken any interfering concomitant medications;
- Did not attend the Week 12 Visit;
- Missed more than 1 post baseline study visit prior to Week 12;

- Have not been compliant with the dosing regimen (i.e., Patients may not miss more than five consecutive days of dosing and must take 80-120% of expected doses. The number of expected doses will be determined for each Patient based on the length of their participation in the study);
- Out of visit window (± 4 days) at the 12-week Visit.

Patients that discontinue from the study due to an AE related to study treatment or documented lack of treatment effect will be included in the PP population. Data for these Patients will not be imputed by multiple imputation but rather their data will be imputed with values consistent with their status as treatment failures. Prior to breaking the blind, other additional criteria may be added to the list to accommodate for unforeseen events that occurred during the conduct of the trial that result in noteworthy study protocol violations.

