8. STATISTICAL AND ANALYTICAL PLANS

8.1 General Methodology

All statistical processing will be performed using SAS® version 9.3 or later unless otherwise stated. Statistical significance will be based on two-tailed tests of the null hypothesis resulting in p-values of 0.05 or less.

The primary method of handling missing efficacy data will be based on estimation using the method of Markov Chain Monte Carlo (MCMC) imputation. The estimation will be done for each treatment group separately so that the pattern of missingness for one group does not influence the estimation of missing data for another group. Groups of complete datasets following the estimation will be concatenated to form analysis datasets for the comparative

analyses and subsequent imputation result inference with SAS PROC MIANALYZE. Descriptive statistics will also be derived from the multiply imputed datasets.

Sensitivity analyses for the primary efficacy endpoints will use 3 methods. For the lesion count endpoint, the first method will use a repeated measures analysis of covariance (ANCOVA), with treatment, analysis center, visit (i.e., Week 2, Week 4 and Week 8), and treatment group by visit interaction as independent factors and a covariate of Baseline. In this analysis, data from all post-baseline visits will be included with no imputation for missing data.

The second sensitivity analyses will use the model based multiple imputation method to impute missing data for the absolute change at Week 12.

The third sensitivity analysis will involve a tipping point analysis.

Similar methods for the dichotomized IGA will involve a repeated measures logistic regression model and a model based multiple imputation and tipping point analysis.

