8.1.5 Handling of Dropouts or Missing Data

Missing data for the ITT population will be estimated by multiple imputation and subsequently analyzed. Missing lesion count and IGA data will be derived for the analysis using the method of Markov Chain Monte Carlo (MCMC) multiple imputation. The pattern of missing observations

in each treatment group cannot influence the missing value estimation in the other group because the imputation will be conducted independently for each treatment group.

Last observation carried forward (LOCF) will be used to impute missing data for the efficacy analyses using the Per Protocol (PP) population.

Patients that discontinue from the study due to an AE related to study treatment or documented lack of treatment effect will be included in the PP population. Data for these subjects will not be imputed by multiple imputation or LOCF but rather their data will be imputed with values consistent with their status as treatment failures. For these subjects, values for lesion count and IGA will be imputed such that change from Baseline is zero, meaning the values will be set to the Baseline value. This imputation will be done after the data for all subjects has been through the MI process.

Incomplete start and end dates for medications will be imputed. Other safety data will not be imputed and will be summarized on an observed case basis.

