8.4.3 Safety Population

All subjects in the randomized population who are presumed to have used the study product at least once and who provide at least one post-baseline safety evaluation will be included in the Safety population and will be analyzed according to the treatment they received. Presumed to have used study product will be defined as having at least one confirmed application of study medication. All safety analyses will be performed using the Safety population.

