Number of Subjects Included in the ITT Population	xx (xx.x%)	xx (xx.x%)	xx (xx.x%)
Number of Subjects Excluded from the ITT Population	xx (xx.x%)	xx (xx.x%)	xx (xx.x%)
Reason Excluded from the ITT Population			
Not Dispensed Study Drug	xx (xx.x%)	xx (xx.x%)	xx (xx.x%)
Number of Subjects Included in the Safety Population	xx (xx.x%)	xx (xx.x%)	xx (xx.x%)
Number of Subjects Excluded from the Safety Population	xx (xx.x%)	xx (xx.x%)	xx (xx.x%)
Reasons Excluded from the Safety Population ^a			
No Documented use of Study Drug	xx (xx.x%)	xx (xx.x%)	xx (xx.x%)
No Post-Baseline Safety Assessment	xx (xx.x%)	xx (xx.x%)	xx (xx.x%)
Number of Subjects Included in the PP Population	xx (xx.x%)	xx (xx.x%)	xx (xx.x%)
Number of Subjects Excluded from the PP Population	xx (xx.x%)	xx (xx.x%)	xx (xx.x%)
Reasons Excluded from the PP Population ^a			
Not Included in ITT Population	xx (xx.x%)	xx (xx.x%)	xx (xx.x%)
Violated Inclusion/Exclusion Criteria	xx (xx.x%)	xx (xx.x%)	xx (xx.x%)
Used Interfering Concomitant Medication	xx (xx.x%)	xx (xx.x%)	xx (xx.x%)
Did not Attend Week 12/ET Visit	xx (xx.x%)	xx (xx.x%)	xx (xx.x%)
Missed More Than 1 Post-Baseline Visit Prior to Week 12	xx (xx.x%)	xx (xx.x%)	xx (xx.x%)
Not Compliant with Dosing Regimen ^b	xx (xx.x%)	xx (xx.x%)	xx (xx.x%)
Week 12/ET Visit Out of Window (+/-4 days)	xx (xx.x%)	xx (xx.x%)	xx (xx.x%)
Other	xx (xx.x%)	xx (xx.x%)	xx (xx.x%)

^a Table includes primary reason (assigned in order presented in table) for reason subject was excluded.

^b Subjects lost to follow-up not included. A subject was considered compliant with the dosing regimen if the subject applied 80-120% of the expected number of applications and did not miss more than 5 consecutive applications while enrolled in the study.

SOURCE: USERNAME\SPONSOR\PROJECT\JOBNAME (DATE,TIME)

Table 14.0.2.2: Summary of Subject Evaluability by Analysis Center and Investigational Site
 (All Randomized Subjects)
 (Page 1 of xx)

Analysis Center	Investigational Site	Number Randomized	E-BPO/E-ATRA 3%/0.1% Cream			Vehicle Cream		
			ITT	PP	Safety	ITT	PP	Safety
xx	xx	xx	xx	xx	xx	xx	xx	xx
xx	xx	xx	xx	xx	xx	xx	xx	xx
	xx	xx	xx	xx	xx	xx	xx	xx
xx	xx	xx	xx	xx	xx	xx	xx	xx
xx	xx	xx	xx	xx	xx	xx	xx	xx
	xx	xx	xx	xx	xx	xx	xx	xx
	xx	xx	xx	xx	xx	xx	xx	xx

SOURCE: USERNAME\SPONSOR\PROJECT\JOBNAME (DATE,TIME)

Table 14.1.1.1: Summary of Subject Demographic Characteristics
(Intent-to-Treat Population)
(Page 1 of 2)

	E-BPO/E-ATRA 3%/0.1% Cream (N=xxx)	Vehicle Cream (N=xxx)	Total (N=xxx)	P-Value

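### The safety population can leave out exposed patients who do not return by about Day 15, and possibly a recorded adverse event with them, because it requires a post-baseline evaluation and a confirmed application

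*Protocol*

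**What the plan says.** Protocol 17.1.4 sets two conditions for the safety population: randomized patients must be "presumed to have used the study product at least once and who provide at least one post-baseline safety evaluation". SAP 8.4.3 repeats both and then defines the first: "Presumed to have used study product will be defined as having at least one confirmed application of study medication". The same section adds that "All safety analyses will be performed using the Safety population".

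Table 14.0.2.1 treats the two conditions as separate grounds for exclusion. One row is for lack of documented use and another is "No Post-Baseline Safety Assessment".

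SAP section 10 lists the changes from the protocol's planned analyses. The move from presumed to confirmed use is not among them. SAP section 2 says the SAP prevails where the two documents differ, so the stricter definition governs.

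**The concern.** Both conditions depend on what happens after dosing, and both are hardest to meet for someone who stops early and does not come back.

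This matters more here than in many trials because of how local reactions become AEs. Under Protocol 14.1 and 14.2, erythema, scaling, dryness, pigmentation change, itching, burning and stinging are recorded as AEs only if they lead to interruption, discontinuation or a new medication. The AE tables therefore capture local intolerance largely through patients who interrupt or stop. SAP section 4 reports application site dryness, exfoliation and pain among the most common events in Phase 2.

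Safety is one of the two primary objectives (Protocol section 7, SAP 5.1). A denominator that can lose early stoppers is a weak basis for comparing AE incidence between arms.

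**Working it through.** The plan states no figure on this point, so the check compares passages and then sizes the effect under stated assumptions.

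**1. When the evidence arrives.** Dosing is at home before bed (Protocol 16.5). The first scheduled post-baseline visit is Week 2, Day 15 ± 3, that is Day 12 to 18. The diary is reviewed there but not collected (12.13). Diary and first pump come back at Week 4 (12.14). For a patient who never returns, neither the routine safety assessment nor the routine proof of application reaches the site.

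**2. The SAP expects such patients.** SAP 8.1.2 provides for a first-application date that is unknown because the patient was lost to follow-up.

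**3. The defaults conflict.** Under SAP 8.8.2, an AE is treatment-emergent unless it is marked as occurring before first application, so use is assumed. Under 8.4.3, use must be confirmed. The SAP can thus call an event treatment-emergent and then exclude the patient for want of confirmed treatment.

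**4. Known use is not enough.** Because Table 14.0.2.1 has two separate exclusion rows, a patient with documented use can still be excluded for lack of a post-baseline assessment.

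**5. A recorded AE may go too.** Protocol 15.2 accepts spontaneous AE reports. Neither document says whether a report without an attended visit counts as a post-baseline safety evaluation.

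**6. How many patients.** Planned N is 280 active and 140 vehicle (Protocol 17.1.4). No early-loss rate is given; assume 2% to 5%.

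- Active: 0.02 × 280 = 5.6 and 0.05 × 280 = 14, so about 6 to 14.
- Vehicle: 0.02 × 140 = 2.8 and 0.05 × 140 = 7, so about 3 to 7.

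**7. Effect on a reported rate.** Let e be the fraction lost, r the fraction of them with a recorded AE, and 10.0% an assumed AE rate in retained patients. With the lost patients put back, the rate is (1 − e) × 10.0% + e × r.

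| e | r = 0% | r = 10% | r = 50% | r = 100% |
|---|---|---|---|---|
| 2% | 9.8% | 10.0% | 10.8% | 11.8% |
| 3% | 9.7% | 10.0% | 11.2% | 12.7% |
| 5% | 9.5% | 10.0% | 12.0% | 14.5% |

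For example, at e = 3% and r = 0, 0.97 × 10.0% = 9.7%. The current tables would show 10.0% in every cell. Whether that is too high or too low depends on r, which the documents do not give.

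**The case against.** The strongest reply concerns the undefined term. SAP 7.2 lists AE reporting among the ways safety is assessed. A patient who telephones to say the cream burned has supplied post-baseline safety information and has, in effect, confirmed an application. On that reading the patient stays in the safety population. Only patients with no recorded AE are excluded, and the r = 0 column applies. This stands as a reasonable reading, but it is not written down, and Table 14.0.2.1 speaks of an assessment.

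The plan also has other routes to the data. Early terminators are asked to complete the final-visit procedures. Patients who stop for an AE are followed up, and loss to follow-up needs at least two calls and a certified letter (Protocol 12.2). Unscheduled visits record AEs (12.16). These routes shrink the affected group. No population definition recovers an AE that nobody reported.

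Requiring documented use is also a common way to keep never-users from diluting AE rates. That is a fair trade-off argument for the use condition. It does not support the separate evaluation condition.

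A reader might go further and infer that early stoppers vanish from the safety record altogether. They do not. Table 14.0.1 gives discontinuation reasons, including AE, by arm for all randomized patients. Table 14.0.2.1 counts the exclusions by arm and reason. SAP 8.4.1 promises listings for all randomized subjects, and the planned listings cover treatment-emergent AEs, serious AEs and discontinuations due to AEs. What is lost is the place in AE incidence and in the Fisher comparison.

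**Conclusion.** The point holds as a wording defect with a cheap remedy. Patients exposed to the product can be left out of all 14.3.x tables because of what happens after dosing. The SAP tightens the use criterion without declaring it, and its treatment-emergent rule assumes the opposite default. Whether a recorded AE is also lost depends on an undefined term.

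The size is unknown. The 2% to 5% loss and the 10.0% AE rate are assumptions, not figures from the documents. The rule applies equally to both arms, so a reader who infers that active-arm AE rates are understated goes beyond the text; that direction is possible but not shown.

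A second tempting inference is that efficacy takes credit for the patients whom safety drops. It is true that "The ITT population will consist of all randomized Patients who were dispensed study product", that "Missing data for the ITT population will be estimated by multiple imputation and subsequently analyzed", and that "The estimation will be done for each treatment group separately". But vehicle patients are imputed in the same way, and tipping-point analyses are planned for the primary endpoints (SAP 8.7.2). The treatment-failure rule for related-AE discontinuations is written for the per-protocol population, and its reach into ITT is unclear (SAP 8.1.5). This is a separate question that changing the safety population would not settle.

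**What to change.** In Protocol 17.1.4 (and the synopsis) and SAP 8.4.3:

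- Delete the post-baseline safety evaluation condition.
- Restore presumed use and define it: product was dispensed, unless the returned pump, the diary or the patient's own statement shows that it was never applied. Any report of use, or any AE not marked as before first application, keeps the patient in.
- State that every recorded treatment-emergent AE is tabulated.
- Keep the visit-wise cutaneous and tolerability tables as observed cases.
- Keep the count of patients with no post-baseline assessment, by arm, as a disposition row instead of an exclusion reason, and align Table 14.0.2.1.
- Record the change in SAP section 10.

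This needs no new data or visits and leaves the efficacy analyses untouched. The cost is that silent non-returners enter the AE denominators: at an assumed 3% lost, the 10.0% rate reads 9.7%. The disposition row lets the reader see how much dilution there is.

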17.2 Study product Evaluations and Analyses

Inflammatory and non-inflammatory lesion count will be recorded for each Patient at Baseline and at Weeks 2, 4, 8, and 12. The absolute and percent change from baseline of inflammatory lesions will be derived for each Patient at Weeks 2, 4, 8, and 12.

The IGA will be recorded for each Patient. The IGA will be dichotomized into “success” and “failure” at Weeks 2, 4, 8, and 12 with a Patient considered a success for those visits if the IGA is at least 2 grades less than baseline and are Clear or Almost Clear.

Patients will be asked to complete PRO questionnaires at appropriate time points.

All statistical analysis will be conducted for both PP and ITT population.

17.3 Assessment of Efficacy

Primary, secondary, and supportive efficacy analyses will be conducted on the ITT (primary) population. Primary efficacy analyses will be conducted on the PP (supportive) population.

17.3.1 Primary Efficacy

There are two co-primary efficacy endpoints:

- Proportion of Patients with an assessment of clear or almost clear and with at least a 2-grade improvement in IGA from baseline at Week 12.
- Absolute change from Baseline in lesion count on the face at Week 12 (separately for inflammatory and non-inflammatory lesions).

17.3.2 Secondary Efficacy

The secondary efficacy endpoints will be the following:

- Percent change from Baseline, in non-inflammatory lesion count at Week 12.
- Percent change from Baseline, in inflammatory lesion count at Week 12.
- Proportion of patients in the E-BPO/E-ATRA cream arm compared to vehicle control achieving at least a 4-point reduction on Item 1 (pimples) of the PRE-FACE from Baseline to Week 12.

- Proportion of patients in the E-BPO/E-ATRA Cream arm compared to vehicle control achieving at least a 4-point reduction on Item 5 (embarrassment) of the PRE-FACE from Baseline to Week 12.
- Absolute change from Baseline, in non-inflammatory lesion count at Week 8.
- Absolute change from Baseline, in inflammatory lesion count at Week 8.
- Absolute change from Baseline, in non-inflammatory lesion count at Week 4.
- Absolute change from Baseline, in inflammatory lesion count at Week 4.

17.3.3 Supportive Efficacy

Supportive efficacy endpoints include the following:

- Proportion of Patients with an assessment of clear or almost clear and with at least a 2-grade improvement in IGA at Weeks 2, 4 and 8.
- Absolute change from Baseline in inflammatory and non-inflammatory lesion counts from Baseline to weeks 2, 4 and 8.
- PRE-FACE ASD: Mean absolute change in PRE-FACE ASD scores from Baseline to Weeks 2, 4, and 8.
- PRE-FACE AID: Mean absolute change in PRE-FACE AID scores from Baseline to Weeks 2, 4, and 8.
- Proportion of Patients in treatment relative to control who report at least “minimally improved” as measured by the PGI-C at Week 12.
- Patient Global Impress of Symptom Severity (PGI-S) at Week 12.
- Patient Global Impression of Treatment Satisfaction (PGI-TS) at Week 12.

17.3.4 Exploratory Endpoint

The mean change in Acne-QoL domain scores from Baseline to Week 12.

17.4 Statistical Hypothesis Testing

17.4.1 Test of Superiority for Lesion Count Variables

This section provides the basic model and statistical approach which is used in combination with the multiple imputation procedures described in Section 18.4.6. Tests of superiority for the absolute change from Baseline in inflammatory lesions will be based on either parametric or non-parametric methods consistent with the statistical assumptions required to support the analyses. Specifically, the tests of superiority will be based on an ANCOVA with factors of treatment and analysis center and the respective Baseline lesion count as a covariate or on ranked data submitted to an ANCOVA with factors of treatment and analysis center and the respective Baseline lesion count as a covariate. If the treatment-by-analysis center interaction effect is significant at an alpha less than 0.10, then the effect will be included in the model; otherwise it will be removed.

A skewness test, based on the methods presented by [J.H. Zar \(1984\)](#), will be applied to the residuals resulting from an ANCOVA. A two-sided p-value for the skewness test significant at 0.01 will imply the use of the non-parametric method. If a parametric analysis is indicated, the results of the parametric analysis will be considered the primary analysis. Should a non-parametric analysis be indicated, the absolute or percent

changes in inflammatory lesions will be rank transformed prior to submitting them to the ANCOVA. Results of the rank-transformed analyses then will be considered the primary analysis; however, results of the non-ranked transformed analyses will also be presented.

